5.13.4 STATISTICAL ANALYSIS OF DATA

In general, the statistics for numerical variables shall be presented as mean \pm standard deviation, median, minimum and maximum values (range), and sample size (continuous data). Categorical data will be presented as counts (numbers) and percentage of the total (rate). In addition, 95% confidence intervals will be presented for the fusion and adverse events rates. Furthermore, subgroup summary statistics will be calculated where necessary.

Where adequate, comparison between subgroups (*e.g.*, with/without mild stenosis; with/without prior discectomy) shall be presented with differences (*e.g.*, P-values). It should be noted that comparisons between subgroups are supportive analyses; these p-values will not be adjusted for multiplicity.

Adverse events (AE) data will be listed individually and summarized. Overall AE results will be presented both on a per-subject basis and per-event basis (*i.e.*, total number of subjects with each event and total number of events reported).

Results of AE seriousness and device-relatedness will be presented as well.

The report of AEs based on specific type of event will be according to the following AE terms, listed in the table below, and in accordance with FDA list of risks applicable for pedicle screw spinal systems (FDA's Executive Summary, Table 11).

ADEVERSE EVENTS
Implant Malposition
Implant Loosening
Device Breakage
Construct Disassembly
Bone Fracture
Graft Settling/Displacement
Loss of Correction
Pseudoarthrosis
Bleeding/Vascular Injury
Neurologic Injury
Back/Leg Pain (Radiculopathy)
Dural Tear/CSF Leak
Wound problems
Infection/Sepsis
Skin Irritation
Cardiac
Respiratory
Gastrointestinal
Reoperation/Revision
Death

In addition, as per the FDA recommendation, the adverse events will be further analyzed according to the Adverse Events table provided in **Section 5.14.4.2**.

Patients who withdraw from the study (following implantation of the investigational device), are lost to follow-up, or for whom data is missing, will be analyzed individually based on the information already available for the patient. In general, if sufficient data will be available for the patient based on previously gathered

information (*e.g.*, at previous follow-up sessions) or if, in cases where fusion occurs prior to withdrawal and no adverse events have been observed, the patient may be regarded as a success.

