5.8 MISSING DATA

Incomplete information may be available for a subject for various reasons:

- Subject stopped participation in the study at its own request;
- Continuing the follow-up is not possible/subject lost to follow-up;

Subject stopped participation in the study at the Investigator's discretion.

In general, in cases where information will be available for a certain missing data point from a previous and from the next follow-up, an interpolation of the values shall be performed. Missing data from patients that were lost to follow-up will be handle by "last value carried forward" approach (*i.e.*, the last value obtained from a subject will be used for the analysis).

5.9 **PROCEDURES**

5.9.1 **PREOPERATIVE MANAGEMENT**

- a. The Investigator will select the subjects according to the inclusion and exclusion criteria, as described in Sections 5.3 and 5.4, respectively.
- b. The Investigator will be acquainted with the technique and instrumentation required for the procedure. Training will be provided by the Sponsor or its authorized representatives in accordance with the Training Protocol (**Appendix C**).
- c. The Investigator will be familiar with the Protocol of the clinical trial.
- d. Signed written Informed Consent must be obtained for all subjects.
- e. The patients shall be instructed to refrain from the use of NSAIDS for two weeks prior to surgery.
- f. All female subjects who are of child bearing age should present a negative beta-HCG blood (pregnancy) test or submit a signed statement that she is using at least one conventional contraceptive method and that to the best of her knowledge she is not pregnant. Such woman shall be informed of the risks involved in participating in the study while pregnant and cautioned to inform the study personnel if she becomes pregnant during the timeframe of the study.

Pre-procedure assessment will be conducted according to the outline provided in the Case Report Forms (CRFs) booklet.

Pre-procedure examination includes (refer also to Table 8 below):

- Demographic data
- > Full medical history, including concomitant medications

- Physical examination
- Neurological examination
- ➢ X-Ray evaluation

The results of the said examinations shall be recorded.

During the pre-operative session, the following forms shall be completed (refer also to **Table 9** below):

- > Pre-operative CRF

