The **motor evaluation** measures the muscle strength in major muscle groups (Gluteus Maximus (hip extension); Iliopsoa (hip flexion); Quadriceps (knee extension); Hamstrings (knee flexion); Anterior Tibial Group (ankle dorsiflexion); Extensor Hallucis Longus (great toe extension); Posterior Tibial (ankle plantar flexion/eversion); and Flexor Halluces (great toe flection)). Muscle strength is evaluated on a 6-point scale ranging from 0 to 5 according to the following key

describing the ability of the patient to move the lower extremities against resistance provided by the examiner:

- ▶ 0 no movement;
- ▶ 1- muscle contraction;
- > 2 lateral movement;
- ➤ 3 against gravity;
- ➤ 4 against moderate resistance;
- \blacktriangleright 5 against full resistance.

Light-touch will test **sensation** for all lumbar and sacral dermatomes in comparison to the contralateral site. The sensation shall be graded as equivalent (normal), impaired, absent, as compared to the contralateral side.

Reflexes (Patella and Achilles) are evaluated according to Bate's Reflex Scale (a 5-point scale ranging from 0 to 4) as follows:

- > 0 − no reflex;
- > 1 somewhat diminished, low normal;
- \triangleright 2 average, normal reflex;
- > 3 brisker than average;
- ➤ 4 very brisk, hyperactive.

Straight leg raising is assessed by measurement of the degree of movement required to reproduce symptoms. A positive test is considered when the patient reports worsening of pain between 30 and 70 degrees of hip passive flexion while knee is extended.

Tenderness will be evaluated by palpation of the lower spine area – lumbar paraspinal region, lumber spinous process, sacroiliac joint, and sciatic notch. Tenderness shall be graded as negative or positive (*i.e.*, palpation provokes painful sensation).

 Patient Success –

Individual patient success with respect to *safety* is defined as:

- No worsening in neurological status (motor, sensory, reflex, straight leg raising, and tenderness assessments) and no new permanent neurological deficits present for at least 2 successive visits at or beyond 6 months (out to 24 months);
- Absence of device-related serious adverse events through 24 months;
- Absence of subsequent surgical interventions at the index level through 24 months.

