5.12 STUDY SUCCESS CRITERIA

The results of the study at 12 months and 24 months postoperatively for all participating subjects will be evaluated, with reference to the reported results from the

literature, as summarized in **Section 5.2.1**. In addition, assessment of success rate will be conducted at each time point, as applicable.

In addition to evaluating individual patient success as the primary composite endpoint, each element of the composite will be evaluated individually as secondary endpoints, as described below.

Fusion – Success for the fusion outcome measure will be defined as two year fusion rate comparable to the two and one year fusion rates presented in the literature. The pooled results of the Company literature research (for patients with DDD treated with pedicle screws with PLIF/ALIF/TLIF and/or PLF), as presented in **Section 5.2.1**, demonstrated at 12 and 24 months postoperatively fusion rates in the different studies ranging from 77% to 97%.

As discussed in **Section 5.2.1.A**, the weighted average for the fusion rate of the ten articles is 87.79%. Based on the literature, we believe our fusion rate will be 88%.

The assumed fusion rate of 88% has a 95% confidence interval of $\pm 6.4\%$ for 100 patients. Notably, the lower bound of this confidence interval, 81.6%, is within the range of the fusion rates reported in the selected literature.

Safety – Success with regard to safety outcome measure is defined as no worsening in neurological status (motor, sensory, reflex, straight leg raising, and tenderness assessments) and no new permanent neurological deficits (present for at least 2 successive visits at or beyond 6 months), absence of device-related serious adverse events, and absence subsequent surgical interventions at the index level, through 24 months, comparable to neurological deficit, device-related serious adverse events, and subsequent surgical interventions rates presented in the literature.

Based on the literature review in FDA's Executive Summary, the rate of these events in the literature control is 13.5%.

Therefore, the Company estimates that the adverse event rate for these events will be 13.5%. With a sample size of 100 patients, this adverse event rate has a 95% confidence interval of $\pm 6.7\%$.

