5.13.3 ANALYSIS POPULATIONS

Intent-to-Treat ("ITT"): All patients treated with the device.

Per-Protocol ("PP"): All patients who did not have a major protocol violation and who completed all study visits.

The primary analysis will be based upon the ITT population. Additional analyses using the PP population will also be presented in the final report.

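### The 24-month safety rate set against 13.5% is a crude percentage in which a patient lost while event-free can be counted as event-free to month 24, with no censoring-adjusted estimate beside it

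*Combined protocol and SAP*

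**What the plan says.** Section 5.10.3 defines safety success over a fixed horizon. It requires freedom from device-related serious adverse events through 24 months, together with "Absence of subsequent surgical interventions at the index level through 24 months" and "no new permanent neurological deficits present for at least 2 successive visits at or beyond 6 months (out to 24 months").

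Section 5.12 judges this outcome by whether it is comparable to a literature rate of 13.5%, and gives the expected precision: "With a sample size of 100 patients, this adverse event rate has a 95% confidence interval of" ±6.7%. Section 5.2.1 D builds the 13.5% by adding event percentages and states no follow-up time for them.

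The planned estimate, in 5.13.4, is a count and a crude percentage with a 95% confidence interval: "Categorical data will be presented as counts (numbers) and percentage of the total (rate"). On the analysis set, 5.13.3 says: "The primary analysis will be based upon the ITT population", where ITT means all treated patients. It adds a per-protocol set: "All patients who did not have a major protocol violation and who completed all study visits".

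Two rules cover incomplete follow-up. For patients lost to follow-up, 5.8 says that "the last value obtained from a subject will be used for the analysis". Section 5.13.4 has withdrawn and lost patients assessed one by one. They may count as successes if enough earlier data exist, or in "cases where fusion occurs prior to withdrawal and no adverse events have been observed, the patient may be regarded as a success".

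No Kaplan-Meier, life-table, cumulative-incidence or person-time estimate appears. The adverse event table in 5.14.4.2 splits events into seven intervals up to month 24 but sets out no number at risk.

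**The concern.** The endpoint is an absence of events up to month 24. For a patient who leaves at month 8 with no event, the data say nothing about months 8 to 24. If that patient stays in the denominator and is recorded as a success, 16 unobserved months are treated as event-free. Some such patients would have had an event, so the study's own rate is understated, which favours the device.

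The decision is left to individual judgement in a single-arm study, with no estimate alongside that treats the unobserved time as unobserved. The ±6.7% interval assumes 100 patients all followed to month 24. At stake is how far the observed safety rate can be read as a 24-month risk when it is set against 13.5%.

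**Working it through.** **The plan's own figures reproduce.** From the table in 5.2.1 D (loosening, breakage, disassembly, reoperation/revision, neurologic injury): 0.4 + 1.3 + 0.1 + 10.9 + 0.8 = 13.5%. Half-width at n = 100: 1.96 × √(0.135 × 0.865 / 100) = 0.067, the stated ±6.7%.

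**Inputs for the bias.** The true 24-month risk is 13.5% (5.12). The following are assumptions, since the plan gives none: loss L of 10, 15 or 20%, spread evenly over months 0 to 24 and unrelated to events, and two shapes of risk over time.

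- Constant hazard: F(t) = 1 − exp(−ht), h = −ln(0.865)/24 = 0.00604. Average of F over 0 to 24 months: 1 − 0.135/0.145026 = 0.0691.
- Half the risk perioperative: F(t) = 1 − 0.9325 exp(−h₂t), h₂ = −ln(0.865/0.9325)/24 = 0.00313. Average: 1 − 0.0675/0.07514 = 0.1017.

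**If every event-free loss is counted as event-free to month 24:** crude rate = (1 − L) × 0.135 + L × average F. For example, at L = 0.20 with constant hazard, 0.108 + 0.0138 = 0.1218.

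| Loss | Constant hazard | Half perioperative |
|---|---|---|
| 10% | 12.8% (bias 0.7) | 13.2% (0.3) |
| 15% | 12.5% (1.0) | 13.0% (0.5) |
| 20% | 12.2% (1.3) | 12.8% (0.7) |

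Timing matters somewhat. With constant hazard and all losses at month 6, the rate is 12.5% at 10% loss and 11.5% at 20%.

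**If losses before month 6 are handled differently.** A quarter of evenly spread losses fall before month 6. Average F over 0 to 6 months, written m, is 0.0179 (constant) or 0.0762 (half perioperative).

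- Event-free early losses left out of the denominator: crude / [1 − 0.25L(1 − m)]. The extremes are 0.1317/0.9769 = 13.5% (10% loss, half perioperative) and 0.1218/0.9509 = 12.8% (20% loss, constant), so the bias is 0.0 to 0.7 points.
- Event-free early losses counted as failures: crude + 0.25L(1 − m). The extremes are 0.1284 + 0.0246 = 15.3% and 0.1283 + 0.0462 = 17.5%, above the true risk.

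**Per-protocol set.** If a share f of event patients and g of the others fail to complete all visits, the rate is 0.135(1 − f) / [0.135(1 − f) + 0.865(1 − g)]. With f = g it is 13.5%. With f = 0.2, g = 0.1 it is 12.2%; with f = 0.3, g = 0.1 it is 10.8%; with f = 0.1, g = 0.2 it is 14.9%. It can err in either direction.

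**Kaplan-Meier.** In 20,000 simulated studies of 100 patients under the loss assumptions above, the mean estimate is 13.5% with a half-width of 6.7 to 7.1 points.

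**The case against.** The strongest objection is materiality. The analyses are descriptive, 5.12 sets no margin or test for safety, and a bias of 0.3 to 1.3 points sits well inside ±6.7. That stands, and it is why this is a low-cost improvement and not a threat to the conclusion.

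Second, a reader might infer that the rule always lowers the rate. The documents do not support that. Section 5.13.4 is permissive and applied patient by patient. Fusion is first assessed at 6 months, so the fusion clause cannot cover earlier losses. Section 5.8 speaks of carrying values forward and does not mention events. As shown above, other handling of early losses shrinks the bias or reverses it. What stands is that the rule is discretionary and that the rate is biased low where unobserved time is counted as event-free.

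Third, a reader might infer from the intended 12-month submission (5.7) that IDE patients with 12 months of follow-up will be pooled with OUS patients at 24 months in one crude rate. No text plans this. Section 5.7 fixes the primary safety analysis at 24 months, 5.12 evaluates results by time point, and both treat the OUS 24-month data as supportive.

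Fourth, Kaplan-Meier recovers the true risk only if loss is unrelated to events. Under constant hazard, if 20% or 30% of would-be event patients leave before their event against 10% of the others, it gives about 11.5% or 10.2%. This stands as a limitation to be stated. The crude rate would then be 0.135 × 0.8 = 10.8% or 0.135 × 0.7 = 9.5%, which is further off.

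Fifth, the per-protocol analysis and the interval table already show part of the picture. They narrow the gap, but neither gives numbers at risk or a censoring-adjusted risk.

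**Conclusion.** The point holds as a modest one. The 24-month safety rate is a crude percentage of all treated patients in which a patient lost while event-free can, at the analysts' discretion, count as event-free to month 24. No planned analysis adjusts for the missing time. If every event-free loss is counted that way, the bias is about 0.3 to 1.3 points. This assumes a true risk of 13.5%, 10 to 20% loss spread evenly and unrelated to events, and the two hazard shapes used here. If early losses are not counted as successes it is smaller. It would not by itself change the judgement of comparability.

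A reader might go further and conclude that the comparison with 13.5% is biased as a whole. That is not shown: the comparator is also a sum of crude percentages with no stated follow-up time, so its own distortion is unknown.

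**What to change.** In 5.13.4, add a Kaplan-Meier estimate of the 24-month risk (cumulative incidence with death as a competing event, if deaths occur), with a 95% confidence interval and numbers at risk at 12 and 24 months. Give it for device-related serious adverse events, for index-level subsequent surgery, and for the first of either. Time it from surgery, censor at last contact, and report it beside the crude ITT and per-protocol rates.

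Include the full combined safety event, since that is the figure set against 13.5%, with a stated dating rule for neurological failure, for example the first of the two successive visits. Scheduled visits in the window are only months 6, 12 and 24, so the rule should also cover a deficit first seen at month 24 or at the last visit before loss.

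State that the estimate assumes loss is unrelated to events, and that 13.5% is a sum of crude percentages without stated follow-up time, so the comparison stays approximate.

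Cost: SAP wording and one extra analysis. Section 5.14.4.2 already requires onset dates. The documents do not show whether the separate OUS study recorded them; if it did not, those events can be dated at the visit where first reported. The downside is a slightly wider interval and a possibly less favourable rate.

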Individual patient success (*i.e.*, overall success) is defined as a composite endpoint. A patient will be considered a "success" if all primary effectiveness and safety outcome measures listed above are met. As detailed later in this document, the statistical analyses of the suggested study will be descriptive in nature.

During the clinical investigation, the patients will be evaluated preoperatively (baseline), intraoperatively, at discharge, and postoperatively at 6 weeks, 3 months, 6 months, 12 months and 24 months, and then annually, until the last patient completed 2-year follow-up. Radiographic endpoints will be evaluated by two independent reviewers at an imaging core laboratory (Medical Metrics, Inc., Texas). In the case of a disagreement between the two radiographic assessors, a third independent reviewer will evaluate the radiographic images to adjudicate the findings. In addition, a CT scan will be acquired for subjects in which bridging bone status could not be determined form X-Rays, at each time point starting at 6 months post-operatively.

At each evaluation time point, as applicable, the primary and secondary endpoints shall be evaluated (*e.g.*, pain and function evaluations based on patient questionnaires shall be performed pre-operatively and starting at 6-week follow-up visit; fusion assessment will be made starting at 6-month). Complications and adverse events will be evaluated at each follow-up visits and over the course of the clinical trial. Detailed evaluation schedule is provided in **Table 8**.

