As indicated above, it is believed that at the time all subjects from the IDE study complete one year follow-up, supporting safety data for 24 months will be available for about 45 patients from the ongoing, OUS study.

**Pain - Individual patient, clinically meaningful, improvement with respect to pain is defined as postoperative improvement at 24 months of at least 20 mm on a 100 mm VAS from the baseline level.**

Value of 73% of patients with \geq 20 mm improvement. This value is selected as it is consistent with the performance of the Silhouette Spinal Fixation System reported in P070031.

Function - Individual patient, clinically meaningful, improvement with respect to function is defined as postoperative improvement at 24 months of at least 15 points on the ODI graded on a 100-point scale as compared to baseline assessment.

Value of 55% of patients with \geq 15 points improvement. This value is selected as it is consistent with the performance of the control group reported in P050010.

Individual Patient Success (Overall Success)

Individual patient success (*i.e.*, overall success) will be determined at 24 months and is defined as a composite primary endpoint. An individual subject will considered a success if all of the following criteria are met:

- Presence of continuous bridging bone between the involved motion segment at 24 months, *i.e.*:
 - Presence of interbody bridging bone and absence of radiolucency > 50%; OR
 - Presence of left posterolateral bridging bone; OR
 - Presence of left posterolateral bridging bone.
- No motion on flexion/extension films at 24 months (success is defined as angular motion < 3° and translational motion < 3 mm);

- Improvement of at least 20 mm on a 100 mm VAS from baseline level at 24 months;
- Improvement of at least 15 points on the ODI graded on a 100 point scale at 24 months as compared to baseline;
- ➢ No worsening in neurological status (motor, sensory, reflex, straight leg raising, and tenderness assessments) and no new permanent neurological

deficits present for at least 2 successive visits at or beyond 6 months (out to 24 months);

- > Absence of device-related serious adverse events through 24 months;
- Absence of subsequent surgical interventions at the index level through 24 months.

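### Section 5.13.4 lets a patient who withdraws after fusing, with no adverse event seen, be counted as a success without meeting the full composite, and Section 5.8 does not supply a consistent rule

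*Combined protocol and SAP*

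**What the plan says.** Section 5.13.4 (Statistical Analysis of Data) covers patients who withdraw after implantation, are lost to follow-up or have missing data. They "will be analyzed individually based on the information already available for the patient". Two circumstances are then named in which such a patient may be credited. One is "if sufficient data will be available for the patient based on previously gathered" information, with no definition of what is sufficient. The other is that "in cases where fusion occurs prior to withdrawal and no adverse events have been observed, the patient may be regarded as a success".

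Section 5.2 (Study Design) defines a patient as a success only "if all primary effectiveness and safety outcome measures listed above are met". Section 5.12 (Study Success Criteria) lists the components: radiographic fusion; a VAS gain of at least 20 mm at 24 months; "Improvement of at least 15 points on the ODI graded on a 100 point scale at 24 months as compared to baseline"; the neurological criterion out to 24 months; and no device-related serious adverse event or index-level surgery through 24 months. The study succeeds if the overall success rate is 41%.

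Section 5.8 (Missing Data) gives three separate reasons for incomplete data: "Subject stopped participation in the study at its own request", loss to follow-up, and stopping at the investigator's discretion. A gap between two attended visits is interpolated. The only end-of-study rule is "Missing data from patients that were lost to follow-up will be handle by" last value carried forward, meaning that "the last value obtained from a subject will be used for the analysis". Section 5.13.3 makes ITT, defined as all patients treated with the device, the primary population.

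**The concern.** The crediting rule replaces a seven-item composite with two conditions, fusion and no adverse event so far. Pain and function drop out, and the safety window ends when the patient leaves. It is also discretionary: each case is judged individually, on a standard that is not defined, and the section does not say who decides or when.

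Withdrawn and lost patients stay in the ITT denominator, so whatever status they are assigned enters the primary rate directly. That rate is compared with a fixed 41%, with no confidence bound or margin to absorb a few doubtful classifications. Discretionary credit given once outcomes are known could therefore decide whether the study meets its overall criterion.

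**Working it through.** **1. Crediting route against the composite**

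| Component (Sections 5.2, 5.12) | Required by the crediting route in 5.13.4? |
|---|---|
| Fusion at 24 months | Fusion at some visit before withdrawal |
| VAS gain ≥ 20 mm at 24 months | Not mentioned |
| ODI gain ≥ 15 points at 24 months | Not mentioned |
| Neurological criterion out to 24 months | Only what was seen before withdrawal |
| No device-related serious adverse event through 24 months | Only up to withdrawal |
| No index-level surgery through 24 months | Only up to withdrawal |

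Fusion is first read at 6 months (Section 5.10.1), so up to 24 − 6 = 18 months of the safety window can be unobserved. A patient who leaves just after the 6-month visit cannot have had two successive visits at or beyond 6 months, which the neurological criterion refers to.

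**2. Section 5.8 against Section 5.13.4**

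- *Withdrawn, no later visit.* Interpolation needs a later visit, and carry-forward is limited to patients lost to follow-up. Only the discretionary rule in 5.13.4 remains.
- *Lost to follow-up.* Both sections apply. Take a patient who fused, had no adverse event and had a last ODI gain of 10 points. Carried forward under 5.8, 10 < 15 and the patient fails. Under 5.13.4 the same patient may be credited. No section says which prevails.

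**3. Certain effect per patient**

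One wrongly credited patient adds 100/100 = 1.0 point at n=100. If the outside-US data are not pooled, which Section 5.13.2 leaves open, it adds 100/55 = 1.8 points.

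**4. Illustration against the 41% criterion**

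The plan gives no power, alpha or dropout figure for this criterion, so there is no figure of its own to reproduce. The true rate p, the number of withdrawals d and the number credited c below are all assumptions. The threshold count k is 41 of 100, or 23 of 55 (0.41 × 55 = 22.55).

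- Full data: P(Bin(n, p) ≥ k)
- Uncredited withdrawals fail: P(Bin(n − d, p) ≥ k − c)
- Uncredited withdrawals succeed at rate p: P(Bin(n − c, p) ≥ k − c)

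| n | d | c | p | Full data | Uncredited fail | Uncredited succeed at p |
|---|---|---|---|---|---|---|
| 100 | 10 | 5 | 0.30 | 0.012 | 0.027 | 0.061 |
| 100 | 10 | 5 | 0.35 | 0.125 | 0.188 | 0.311 |
| 100 | 10 | 5 | 0.38 | 0.301 | 0.386 | 0.547 |
| 100 | 10 | 3 | 0.35 | 0.125 | 0.094 | 0.224 |
| 55 | 6 | 3 | 0.35 | 0.179 | 0.239 | 0.348 |

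The bounds for n=100, 10 withdrawals and completers at 35% are P(Bin(90, 0.35) ≥ 31) = 0.583 if all withdrawals count as successes and P(Bin(90, 0.35) ≥ 41) = 0.025 if all count as failures.

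The row with 3 of 10 credited lies on both sides of the full-data value. Even the direction of the effect depends on how uncredited patients are counted, which the plan does not state.

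**The case against.** **Success might mean fusion success only.** The protocol does use patient-success language for single components (Sections 5.10.1 and 5.10.3), and the sentence is loosely built. But Section 5.2 defines patient success as the composite, and a fusion-only rule would not need an adverse-event condition. The ambiguity is real and is itself a reason to rewrite the sentence.

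**The adverse-event condition is strict.** This stands in part. Section 5.14.4.1 counts any untoward occurrence, which is broader than device-related serious events, and reoperation is a listed adverse event. This limits how many patients could be credited. It does not stand in for pain, function or the follow-up that was never observed.

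**The two sections can be read together, with 5.8 supplying the value and 5.13.4 the review.** Possible for patients lost to follow-up, but nothing says so, and it leaves withdrawn patients without a rule.

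**The analysis is descriptive, and other results will be shown.** The per-protocol analysis requires all visits, so it leaves these patients out, and results stratified by US and outside-US sites will also be presented. These may expose the effect but do not remove it from the ITT rate set against 41%. Independent readers and the clinical events committee protect the radiographic and adverse-event inputs, not the final classification.

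**The probabilities rest on assumptions.** This stands. Credited patients are selected for having fused without an adverse event, so their true success rate is probably above p and the illustration probably overstates the inflation. Full data is also a benchmark that no missing-data rule attains.

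**Conclusion.** The concern holds, and the rule must be changed before the data are analysed. As written, Section 5.13.4 contradicts the endpoint definition in Sections 5.2 and 5.12. Section 5.8 does not resolve this: it has no end-of-study rule for withdrawn patients and a different rule for lost ones.

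The part of the size that needs no assumption about dropout is the contribution of each wrongly credited patient to the primary rate, as given in the working. The total cannot be determined from the plan. The illustrations show only that a handful of discretionary classifications can change materially the chance of reaching the threshold. Confidence in the textual finding is high; its one dependence is on reading success as the composite, which is the meaning Section 5.2 gives it.

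**What to change.** - Delete the crediting sentence and the case-by-case classification from Section 5.13.4. If only fusion success was meant, say so and confine the sentence to that component.
- State one prespecified rule, worded identically in Sections 5.8 and 5.13.4, for both withdrawn and lost patients. Under it, no patient is an overall success unless every component, including VAS and ODI, is met, and an observed safety failure or index-level surgery is never overwritten.
- Report how many patients had their status assigned rather than observed, and add at least one sensitivity analysis, such as missing-as-failure.

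The choice of primary rule is the sponsor's, provided it is fixed before the data are seen.

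The cost is wording in two sections, one count and one extra analysis, with no new data. The reported rate may be lower. If the sponsor chose missing-as-failure as the primary rule, which this fix does not require, the loss could be material: at an assumed true 41%, n=100 and 10 dropouts, the chance of reaching 41 successes falls from P(Bin(100, 0.41) ≥ 41) = 54% to P(Bin(90, 0.41) ≥ 41) = 22%.
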